## Sit-to Stand Test (STS)

The STS test is a performance test that requires an individual to rise from a seated position as many times as possible in a 30-second period with the score recorded as the number of repetitions completed. Performance of this test requires the use of various lower extremity muscle groups, including the hip extensors, knee extensors, hip adductors, hip flexors and knee flexors. Each of these muscle groups makes a different contribution depending on the stage of the maneuver. Given that all of the muscle groups required to rise from a seated position are being tested using HHD, improved performance on this measure could be used to translate any observed changes in LEC or the individual lower extremity muscle groups into clinically meaningful benefit to the patient. The ability to rise from a seated position is critical to performance of various daily activities, including toileting and getting out of a car, and is necessary to maintain functional independence.

## Weighted Arm Lift Test (WAL)

The WAL test is a performance test that requires an individual to raise a 1 kg dumbbell over the head from a seated position as many times as possible in a 30-second period with the score recorded as the number of repetitions completed. Performance of this test requires the use of various upper extremity muscle groups, including grip, specifically finger flexors and wrist flexors/extensors, to hold the dumbbell, elbow extensors (and to a lesser extent elbow flexors) to raise the dumbbell and shoulder flexors, deltoids and pectoral muscles to assume and maintain the position of the shoulder during the maneuver. Muscle groups in the trunk and neck are also required for stabilization in the seated position. Improved performance on this measure could be used to translate any observed changes in the UEC into clinically meaningful benefit to the patient since reaching ability is critical to the performance of various activities of daily living and the maintenance of functional independence.

## Knee Extensors

The knee extensors (quadriceps) are widely recognized to be spared in GNE Myopathy relative to other lower extremity muscle groups making it a defining feature of the disease and instrumental in making a differential diagnosis. Dynamometry data from the Phase 2 study showed significant weakness in this muscle group relative to normative data although the magnitude of the weakness was considerably less than in the other lower extremity muscle groups tested. Biopsy data from the Phase 2 study revealed limited pathology suggesting that there was considerable viable muscle tissue remaining in this group. For this reason, strength in the knee extensors, as measured by dynamometry, is included as an endpoint to assess the effect of SA-ER on a relative intact lower extremity muscle group. It should be noted, however, that there can be considerable variability in dynamometry results for this large, intact muscle group, particularly among stronger patients who can overpower the strength of the test administrator during the maneuver.

## Six Minute Walk Test (6MWT)

A comprehensive analysis of the 6MWT data from the UX001-CL201 study suggests that the test may not be appropriate for the assessment of lower extremity function in GNE Myopathy. The majority of the subjects begin wearing AFOs (ankle-foot orthoses) shortly after diagnosis to compensate for the “foot drop” resulting from weakness in the tibialis anterior, the most common presenting symptom. The AFOs, which hold the foot and ankle at a 90 degree angle, limit the flexibility of the foot and ankle while walking. Specifically, they prevent the generation of power during the stepping process that is necessary to propel the body forward. The impact this has on the ability to take longer, more frequent steps could interfere with the ability to detect changes in 6MWT distance even if lower extremity strength is improved. In addition, stability issues resulting from extensive weakness in the hip and knee flexors make patients fearful of falling during walking which can compromise performance on this volitional test. Supportive evidence for this includes two findings. First, while patients were able to walk at 61.0% predicted comfortable walking speed, they were only able to walk at 45.7% predicted during the rapid walking test. Second, 72.7% of patients able to walk  $\geq 200$ m (70% of the patients enrolled) reported frequent falls prior to enrollment. Given these findings that patients may be unwilling or unable to increase walk distance even with improved strength, the 6MWT is not appropriate for use as a key secondary endpoint in this study.

### 3.4 Study Duration

Individual subject participation in this study will be a maximum of 56 weeks, including up to 4 weeks between Screening and Baseline visits, a treatment duration of 48 weeks, and a Safety Follow-up Visit occurring 4 weeks after last study drug administration. Subjects who complete the study may be eligible to participate in an open-label extension study.

All subjects will be randomized to receive 6 g/day SA-ER or placebo during the 48-week Treatment Period. The 48-week treatment duration is also intended for collection of safety

data on the SA-ER tablets for long-term use and to provide sufficient insight on sustained clinical effects and improvements in adult GNEM patients.

### 3.5 Stratification Factors

Subjects will be enrolled in the study and sequentially assigned an identification number. Approximately 80 eligible subjects will be randomized via an Interactive Web Randomization System (IWRS) and assigned in a 1:1 ratio to receive 6 g/day of SA-ER or matching placebo for 48 weeks. Randomization of subjects will be stratified by gender with a planned enrollment of no more than 60% of subjects of either gender.

### 3.6 Randomization, Blinding

The study will be conducted as a randomized, double-blind, placebo-controlled study. Double-blind conditions will be established so that neither the study team, subject, or site personnel involved in study conduct will know the identity of a subject's treatment. Study parameters to achieve and maintain the double-blind status of the study include:

- Sequential assignment of subject numbers
- Management of subject treatment assignment via an IWRS
- Labeling of study drug with the study number and a unique kit number
- Packaging and delivery of study drug supplies to sites in a manner that maintains blinding of site personnel
- Matched appearance of investigational product and placebo

The Investigator and site personnel will remain blinded to the randomization treatment assignment during the study. Treatment assignment for an individual subject should be unblinded by the Investigator only in an emergency, and only if knowledge of the treatment assignment is urgently needed for the clinical management or welfare of the subject. Treatment should be provided in accordance with the medical condition and with regard to the information provided in the IB. The Investigator should contact the medical monitor or project manager before unblinding, when possible, but priority should be given to treatment of the subject.

The Investigator must record the date and reason for revealing the blinded treatment assignment for that subject in the IWRS and in the source documents. Treatment assignment may be unblinded by the Sponsor to satisfy expedited safety reporting requirements of regulatory authorities. The system to unblind an assignment will be maintained and executed through an IWRS which will be available 24 hours a day, 7 days a week.

### 3.7 Determination of Sample Size

The design and analysis of this study is intended to provide sufficient data to evaluate clinical efficacy of SA-ER.

Based on the results of the Phase 2 study (UX001-CL201), approximately 80 subjects will be randomized in this Phase 3 study. This sample size will provide 90% power to detect a difference of 5 kg in the UEC score change from baseline using a t-test between the SA-ER treatment and the placebo group, assuming a standard deviation of 6, and a two-sided alpha of 0.05.

### **3.8 Interim Analysis**

No interim analysis is planned.

### **3.9 Data Monitoring Committee**

An independent DMC with appropriate expertise in the conduct of clinical trials will act in an advisory capacity to monitor subject safety on a routine basis throughout the trial. A review of blinded safety data will be conducted by the DMC at least twice per year, with the first meeting scheduled once the first subject has been enrolled. Ad hoc meetings will be held if indicated based on observed events. The DMC may also provide advice to Ultragenyx in any determination of whether study enrollment should be paused or if the study should be halted.

The responsibilities of the DMC will be defined in a DMC charter.

## 4 STUDY CLINICAL OUTCOMES AND COVARIATES

All data are collected according to the schedule of assessments included in the protocol. Efficacy will be evaluated by changes in upper and lower extremity muscle strength and function, and self-reported physical functioning. Results from baseline assessments will be compared with those of post-treatment assessments, with efficacy conclusions based on change from baseline over the treatment period in comparison with placebo.

### 4.1 Primary Clinical Efficacy Endpoint

Upper Extremity Composite Score: Muscle strength based on the maximum voluntary isometric contraction (MVIC) against a dynamometer will be measured bilaterally in the following upper extremity muscle groups: gross grip, shoulder abductors, elbow flexors, and elbow extensors. The UEC is derived from the sum of the average of the right and left total force values (measured in kg).

### 4.2 Key Secondary Clinical Efficacy Endpoints

- Lower Extremity Composite Score: Muscle strength based on MVIC against a dynamometer will be measured bilaterally in the following lower extremity muscle groups: knee flexors, hip flexors, hip extensors, hip abductors and hip adductors. The LEC is derived from the sum of the average of the right and left total force values (measured in kg).
- Muscle strength in knee extensors: bilateral total force defined as the average of the right and left force values (measured in kg).
- GNEM Functional Activities Scale Mobility: Lower extremity use and function will be assessed using the Mobility domain of the GNEM-FAS instrument a disease-specific measure developed to assess the functional impact of changes in muscle strength on mobility (reflective of the lower extremities).

### 4.3 Other Secondary Clinical Efficacy Endpoints

- GNEM Functional Activities Scale Upper Extremity Score: Upper extremity use and function will be assessed using the Upper Extremity domain of the GNEM-FAS instrument, a disease-specific measure developed to assess the functional impact of changes in upper extremity muscle strength.
- Number of Stands in the Sit-to-Stand Test: Lower extremity function will be assessed using a sit-to-stand test. The number of times the subject can rise from a seated to a standing position in a 30-second period will be recorded.
- Number of Lifts in the 30 second Weighted Arm Lift Test: Upper extremity function will be assessed using a weighted arm lift test performed bilaterally. The number of times the subject can raise a 1 kg weight above the head in a 30-second period will be recorded.

- Meters Walked in the Six-Minute Walk Test: The total distance walked (meters) in a six minute period (6MWT) will be measured as well as the percent predicted distance based on normative data for age and gender.

#### 4.4 Tertiary Efficacy Endpoints

- Upper Extremity Composite Percent Predicted: The percent predicted total force values will be determined based on reference equations adjusting for age, gender, height, and weight. The percent predicted force will be calculated for each side and the bilateral percent predicted values will be averaged for each upper extremity muscle group. The mean of the four averages in percent predicted scores will be calculated for each subject to create a percent predicted UEC score, and analyzed relative to baseline to create a UEC mean change in percent predicted score.
- Lower Extremity Composite Percent Predicted: The percent predicted total force values will be determined based on reference equations adjusting for age, gender, height, and weight. The percent predicted force will be calculated for each side and the bilateral percent predicted values will be averaged for each lower extremity muscle group. The mean of the five averages in percent predicted scores will be calculated for each subject to create a percent predicted LEC score, and analyzed relative to baseline to create a LEC mean change in percent predicted score.
- Muscle strength (Total Force in kg)) for Each Individual Muscle Group: Bilateral total force for each individual muscle group included in the UEC and LEC will be reported.
- Percent Predicted in Each Individual Muscle Group: Bilateral total force for each individual muscle group included in the UEC and LEC.
- Percent of Predicted Muscle Strength in Each Individual Muscle Group: Bilateral percent predicted total force for each individual muscle group included in the UEC and LEC.
- Percent Predicted in knee extensors: Bilateral percent predicted total force of knee extensors.
- Total Score on the GNEM-FAS
- Self-Care Domain Score on the GNEM-FAS
- Individual Neuromuscular Quality of Life Questionnaire: A 45-item self-report questionnaire with 4 domains on the impact of key muscle disease symptoms on the ability to perform basic activities of daily living, functional independence, relationships and overall well-being will be administered. The individual domain scores will be calculated.
- Clinical Global Impression Scale: Investigator assessment of severity of subject's GNEM using the CGI-improvement scale (CGI-I) during treatment, in 3 target areas.
- Creatine Kinase Levels: CK levels in serum will be measured to assess the degree of reduction of CK levels observed as a surrogate for muscle injury.

#### 4.5 Drug Concentration Measurements

- Serum Free Sialic Acid: The change in free SA level.
- Urine Sialic Acid - Free, Total and Bound: Changes from baseline in urine free, total and bound SA levels.

#### 4.6 Urine Testing for ManNAc:

Urine will be tested for the presence of ManNAc to detect compliance with prohibited medication restrictions.

- Changes from baseline in Free ManNAc levels in urine will be analyzed.

#### 4.7 Safety Endpoints

Safety will be evaluated by the incidence and frequency of adverse events (AEs) and serious adverse events (SAEs), including clinically significant changes from study baseline to scheduled time points in the following:

- Interval history
- Vital signs
- Physical examination results
- Clinical laboratory results
- Suicidal ideation and behavior
- Concomitant medications

#### 4.8 Potential Covariates

All models used for each individual clinical endpoint will incorporate the baseline value, gender and region as covariates. Region is comprised of two levels, one that combine all sites in North America, and the other one combines all sites in the rest of the world. Additional covariates may be used and the details will be included in the analysis model.

## 5 DEFINITIONS

### 5.1 Baseline

Baseline is defined as the last assessments prior to or on the date of first dose of investigational product administration. Analyses will indicate if a different baseline value is used.

### 5.2 Drug Compliance

Compliance = total dosage received / total dosage planned \* 100%. Total dose planned is calculated for the period a subject is on investigational product, which is either 48 weeks if a subject completes the study, or the period up to early withdrawal.

### 5.3 Muscle Strength

The highest value of the three measurements collected for each muscle will be used for all HHD endpoints.

- **HHD Individual Muscle Strength Average Score** is calculated as the average of the right and left raw measurements in kg for an individual muscle group: individual muscle strength raw score = (left-side measurement + right-side measurement) / 2. If a value from the right or left side of an individual muscle group is missing, the missing value will be imputed using the non-missing value from the other side.
- **HHD Upper Extremity (UE) Composite Score** is calculated as the sum of the individual muscle strength average scores for the following muscle groups: gross grip, shoulder abductors, elbow flexors and elbow extensors. If a component individual muscle strength raw score is missing, the composite score will not be computed.
- **HHD Lower Extremity (LE) Composite Score** is calculated as the sum of the individual muscle strength average scores for the following muscle groups: hip flexors, hip extensors, hip abductors, hip adductors and knee flexors. Knee extensors will not be included in the calculation of the LE HHD composite score. If a component individual muscle strength raw score is missing, the composite score will not be computed.
- **HHD Total Composite Score** is calculated as the sum of the HHD UE composite score and the HHD LE composite score. If the UE or LE composite scores are missing, the HHD Total Composite Score will not be computed.
- **Predicted Normal HHD Values** will be derived for the raw right/left strength values from bilateral pinch, gross grip, shoulder abductors, elbow flexors, elbow extensors, hip flexors, hip extensors, hip abductors, hip adductors, knee flexors and knee extensors collected at Baseline using the regression equations outlined in Appendix 10.4. Predicted normal HHD scores for derived variables such as individual muscle raw score, UE/LE composite score, and total composite score will use the same computation method for raw

scores as described above but replace the observed values with the predicted normal HHD values.

- **% of Predicted Normal HHD Values** for the individual muscle groups and composite scores will be calculated as follows: (Observed Value / Predicted Normal HHD Value) \*100%. Baseline predicted normal values will be used to derive % of predicted normal values for all post-baseline study time points.
- **% of predicted Total HHD UE and LE values** will be calculated as follows: (Raw strength value/Predicted normal strength value) \*100%. Percent predicted total normal strength value is the sum of percent predicted values of individual muscle groups.

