## 7 DATA SCREENING AND ACCEPTANCE

### 7.1 Handling of Missing and Incomplete Data

Missing clinical outcome data can occur for multiple reasons, including missed patient visits and scales or measures with missing item scores. Missing and incomplete data will be identified through a review of tables and listings for this study. Missing and incomplete data will be identified for investigation, and possible resolution, by Data Management prior to the study database lock.

Missing measurements in HHD individual muscle group test will be imputed as 0 if the reason for missing is due to weakness. When the measurement for one side is missing, the measurement from the other side will be used to impute the missing value. For UEC and LEC, if measurements are missing for both sides while patients are still in study, the composite score will not be computed. Such cases are expected to be limited. Details of missing observation handling in HHD for individual muscle group are provided in [Appendix 10.2](#). The handling of missing data in individual questions in GNEM-FAS can also be found in [Appendix 10.2](#).

In general, randomly missing assessments for an individual subject would remain as missing. The important case for imputation will be those subjects who are in the study for some period of time but decline in function and leave the study, regardless of whether this decline is the reason listed for withdrawal. The GEE method might not adequately cover the projected decline for these subjects and may not be appropriately conservative. In such cases a single imputation method will be used to estimate the change in strength over the remaining time of the study and these imputed values will be used for the GEE analysis.

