## 10.2 Missing Observation in Hand Held Dynamometry and GNEM-FAS

Imputation rules outlined in this section for dynamometry are defined below and are based on the distinct pattern of muscle weakness associated with GNE Myopathy and the features of the dynamometers used in this study. The most common cause of missing data is muscle weakness severe enough to prevent the subject from registering the minimum amount of force against the dynamometer required to obtain a measurement during a maximum voluntary isometric contraction maneuver. In those cases, the value is imputed to 0, and preserves the ability to calculate the UEC and LEC scores. There are some scenarios in which non-random missing HHD data values result in missing UEC and LEC values. When strength in a particular muscle group exceeds the resistance that can be applied by the administrator, a reliable value cannot be obtained from the dynamometer. This is a recognized limitation of a hand-held device (Visser et al. 2003). In GNE Myopathy, the only muscle group at risk for this scenario is the knee extensors, due to the relative sparing of the quadriceps. All other non-random missing HHD data are related to the clinical condition of the subject at the time of the testing where a test may not be administered due to pain, injury, contracture or another extenuating circumstance that could cause discomfort to the subject. The proposed plan for the handling of this data is intended to provide the most accurate estimate of muscle strength and physical function possible based on knowledge of the disease and the outcome measures obtained during the conduct of previous studies.

Missing observations in HHD for individual muscle group will be imputed based on reason for missing and if the muscle strength measurement is missing on both sides or one side. The table below provides a summary of the imputation rule followed by detailed descriptions.

Instrument	Missing Reason	Imputation
HHD missing BOTH sides	Too Weak	0
	Too Strong	NA , UE/LE composite not computed
	Pain	NA , UE/LE composite not computed
	Injury	NA , UE/LE composite not computed
	Contracture	NA , UE/LE composite not computed
	Other	NA , UE/LE composite not computed
HHD missing ONE side	Too Weak	0
	All other reasons	The value from the other side that was measured

*Missing Reason = Weakness*

A value of 0 should be imputed for a W.

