- If both sides are W, a value of 0 is assigned to each side and the muscle group IS counted as part of the UE or LE composite.
- If one side is W, a value of 0 is assigned to that side and the 0 is averaged with the value from the other side. The muscle group IS counted as part of the UE or LE composite.

*Missing Reason = Contracture*

A value of 0 should NOT be imputed for a C. A C is missing data because the test was not performed due to the contracture.

- If both sides are C (which would be rare), then the data for this muscle group is missing and the UE or LE composite will be set to missing.
- If one side is C, then the data is missing from this side and the value from the other side should be used to reflect the total strength for this muscle group. The muscle group IS counted as part of the UE or LE composite.

*Missing Reason = Pain*

A value of 0 should NOT be imputed for a P. A P is missing data because the test was not performed due to pain.

- If both sides are P, then the data for this muscle group is missing and the UE or LE composite will be set to missing.
- If one side is P, then the data is missing from this side and the value from the other side should be used to reflect the total strength for this muscle group. The muscle group IS counted as part of the UE or LE composite.

*Missing Reason = Injury*

A value of 0 should NOT be imputed for an I. An I is missing data because the test was not performed due to pain.

- If both sides are I, then the data for this muscle group is missing and the UE or LE composite will be set to missing.
- If one side is I, then the data is missing from this side and the value from the other side should be used to reflect the total strength for this muscle group. The muscle group IS counted as part of the UE or LE composite.

*Missing Reason = Too Strong*

An S indicates that the test was attempted but that the subject overpowered the administrator and a valid value could not be obtained.

- If both sides are S, then the data for this muscle group is missing and the UE or LE composite will be set to missing.
- If one side is S, then the data is missing from this side and the value from the other side should be used to reflect the total strength for this muscle group. The muscle group IS counted as part of the UE or LE composite.

*Missing Reason = OTHER*

No value should be imputed if there is an O.

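### SAP 5.3 and one sentence of 7.1 fill a missing side with the other side's force without excepting weakness, against Appendix 10.2; for other reasons all three sections allow a spurious change of half the left-right difference.

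*SAP*

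**What the plan says.** SAP 5.3 defines the muscle-group score behind the UEC, the LEC and the knee extensor endpoint: "individual muscle strength raw score = (left-side measurement + right-side measurement) / 2". For a missing right or left value it adds that "the missing value will be imputed using the non-missing value from the other side". It sets no condition on the reason and does not refer to Appendix 10.2.

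SAP 7.1 contains two rules in consecutive sentences. The first: "Missing measurements in HHD individual muscle group test will be imputed as 0 if the reason for missing is due to weakness". The second, again without condition: "When the measurement for one side is missing, the measurement from the other side will be used to impute the missing value". It then sends the reader to Appendix 10.2 for details.

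Appendix 10.2 works by reason. For a too-weak side, "a value of 0 is assigned to that side and the 0 is averaged with the value from the other side". For one side missing for any other reason, the table entry is "The value from the other side that was measured", and separate paragraphs repeat this for contracture, pain, injury, too strong and other. The muscle group still counts in the composite. No section adjusts the copied value for the subject's own baseline left-right difference, or requires the same sides at baseline and follow-up.

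**The concern.** There are two separate issues.

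**Weakness.** Appendix 10.2 treats weakness as a reason for a missing value and states: "The most common cause of missing data is muscle weakness severe enough". A too-weak side therefore falls within the wording of 5.3, which copies the stronger side, while 10.2 scores it 0. The reading chosen can decide whether loss of measurable force counts as gain or decline. SAP section 1 ranks the SAP above the protocol, but nothing ranks SAP sections against each other.

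**Other reasons.** Here the sections agree, so reconciling them changes nothing. Copying the other side's absolute force at one visit, when both sides were measured at baseline, moves the score although strength has not changed. The movement enters the primary UEC and the key secondary LEC and knee extensor endpoints. It could also affect the dropout rule in 7.1, which applies only if the change at the last available visit is negative.

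**Working it through.** **Scale.** SAP 3.7 plans for a 5 kg difference in UEC change, SD 6, two-sided alpha 0.05, about 80 subjects (40 per arm), 90% power. Recomputed power is 96.1% (normal approximation) or 95.7% (t-test), so the 90% is not reproduced. An assumed dropout of about 20% would bring it to 91.5% or 90.7%. That is a separate matter; here the 5 kg and SD 6 only supply a scale.

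**Weakness conflict.** Let R be the measured side, the other being too weak.
- 5.3 read literally: (R + R)/2 = R.
- Appendix 10.2: (R + 0)/2 = R/2. The gap is R/2.
- R = 10 kg: 10 against 5 kg. R = 20 kg: 20 against 10 kg.
- Baseline 10 and 4 kg (average 7), the 4 kg side later too weak and the other still 10: change is 10 − 7 = +3 kg under 5.3 and 5 − 7 = −2 kg under 10.2.

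For the arm mean, one subject in 40 with a 5 kg gap contributes 5/40 = 0.125 kg.

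**False change for other reasons.** Both sides are measured at baseline, one is missing later, and true strength is unchanged. Then

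false change = present side − (present + missing)/2 = (present − missing)/2.

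Baseline 12/10 gives ±1.0 kg and 20/15 gives ±2.5 kg. It is 0 if the sides are equal or the same side is missing at both visits. A side missing at baseline and measured later produces the same kind of error.

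The documents do not give patients' asymmetry, so the only internal guide is the healthy-population equations in Appendix 10.4. Assumed subjects: man aged 35, 80 kg, 1.75 m (weight/height² = 26.12); woman aged 30, 60 kg, 1.63 m (22.58). For the man's elbow flexors:
- right = −0.13×35 + 11.24 + 0.07×26.12 + 22.78 = 31.30 kg
- left = −0.11×35 + 10.63 + 0.05×26.12 + 19.66 = 27.75 kg
- half difference = (31.30 − 27.75)/2 = 1.78 kg

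| Muscle group | Man | Woman |
|---|---|---|
| Elbow flexors (UEC) | 1.78 kg | 1.49 kg |
| Shoulder abductors (UEC; Newtons/9.80665) | 0.63 kg | 0.49 kg |
| Elbow extensors (UEC) | 0.29 kg | 0.26 kg |
| Gross grip (UEC) | no side difference in the norms | same |
| Hip flexors (LEC) | 1.20 kg | 0.74 kg |

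At age 40 (man 75 kg, 1.75 m; woman 62 kg, 1.63 m) elbow extensors give 0.28 and 0.21 kg.

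**Error of the two filling rules.** Let D be the SD of the baseline left-right difference, and 0.7 kg the assumed SD of each side's own change. Change common to both sides cancels.
- Copying the other side: RMSE = √(D² + 2×0.7²)/2 = 0.70, 1.12 and 1.58 kg for assumed D = 1, 2 and 3 kg.
- Own baseline plus the other side's change: RMSE = √(2×0.7²)/2 = 0.49 kg at every D.

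**Trial level (frequencies assumed).** With D = 3 the extra error is 1.5 kg per affected group. If 10% of values are affected in each of four UEC groups, independently, variance rises from 36 to 36 + 4×0.10×1.5² = 36.9 (SD 6.07), and power at 40 per arm falls from 96.1% to 95.7% (normal approximation). A shift in the arm difference needs imbalance. If the share affected in one direction differs by p between arms and sides differ by d, the shift is p×d/2: from 0.05×2/2 = 0.05 kg to 0.20×10/2 = 1.0 kg.

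**The case against.** On weakness, the plan contains its own answer. The first sentence of 7.1 states zero for weakness, 7.1 defers to Appendix 10.2, and 10.2 is explicit: "If one side is W, a value of 0 is assigned to that side". Once that side holds a 0 it is no longer missing when the general sentence in 5.3 applies. A careful programmer would get 5 kg, not 10. This stands. A reader might infer that the planned analysis hides the worst declines; that requires ignoring 7.1's first sentence and all of 10.2. SAP 3.3 also says nearly all tested patients kept residual upper extremity strength, and describes unmeasurable weakness mainly in the lower extremity.

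A reader might also set the 5 kg gap against the 5 kg design difference. The first is one subject's error, the second a difference between group means, so the comparison fails.

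On the other reasons, copying the other side is a deliberate choice, written out reason by reason, and 10.2 says the handling rests on knowledge of the disease and earlier studies. The half-differences come from healthy people, two of the four UEC groups show little or none, and the power loss is small under the assumptions tried. All of this limits the size. It does not remove the error: a fill anchored to baseline has smaller error whenever the sides differ and equal error when they do not.

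**Conclusion.** The drafting conflict is real and should be removed. The definition of the primary score in 5.3, and one sentence of 7.1, give a different result from Appendix 10.2 for a too-weak side: half the measured side's force in that muscle group (5 kg when it reads 10 kg). It is a per-subject discrepancy, resolvable by following 10.2, and probably less common in the UEC than in the LEC.

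The second issue holds under every reading. For non-weakness reasons, a side measured at baseline and missing later produces a spurious change of half the left-right difference: about 1.5 to 1.8 kg for elbow flexors, 0.5 to 0.6 kg for shoulder abductors and 0.2 to 0.3 kg for elbow extensors by healthy-population norms, with none derivable for grip. It is mainly added noise. A reader might infer bias in the treatment comparison, but the documents give neither the frequency of one-sided loss nor the patients' asymmetry, and nothing in them indicates that it would differ by arm. The 0.05 to 1.0 kg range rests wholly on assumed imbalance.

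**What to change.** **Clarification (should be made).** In the one-side sentences of 5.3 and 7.1, add: *except when the reason is weakness, which is scored 0 (Appendix 10.2)*. The cost is two short insertions.

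**Improvement (cheap, worth making).** For every other one-sided loss, set the missing side to its own baseline value plus the other side's change from baseline, floored at 0. The floor is needed because a side at 2 kg paired with a fall of 4 kg would otherwise become −2 kg. If the side was missing at baseline for a non-weakness reason, base that muscle group's change on the other side only.

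Make this edit together in 5.3, 7.1, the Appendix 10.2 table and its five non-weakness paragraphs; changing 5.3 alone would create a new contradiction. It costs these further edits and one derivation step on data already collected. The downside is that later measurements of a side missing at baseline go unused for the change score.
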